Subjects will be screened for enrollment from 4 weeks (28 days) to 2 days (the day before admission) before the study drug administration (Day -28 to Day -2) in Period 1. Subjects will be admitted to the study site on the day before the study drug administration (Day -1) in both Periods 1 and 2, and will be hospitalized under medical supervision for 4 days (until 48 hours after the study drug administration). They will undergo daily examinations from the day before the study drug administration (Day -1) and observations during their hospitalization according to the study schedule specified in [Appendix A](#), and will be discharged from the study site on Day 3 after confirmation of safety by the investigator or sub-investigator. Subjects will return to the study site for follow-up examinations on Day 6. A washout period of at least 6 days will be placed between the study drug administrations in Periods 1 and 2.

Subjects will visit the study site 5 times, including the visit for screening examinations, in this study. They will be hospitalized for a total of 8 days in Periods 1 and 2.

The examinations scheduled on the day before the study drug administration (Day -1) in Period 2 can be replaced with the follow-up examinations (Day 6) in Period 1, if they are scheduled on the same day. If this is the case, the subject will visit the study site 4 times in this study.

A schematic of the study design is included as [Figure 6.a](#). A schedule of assessments is listed in [Appendix A](#).

Figure 6.a Schematic of Study Design (Period 1 and Period 2)

Element	Screening		Treatment (TAK-536 10 mg)*					Day 6
	Day	Day -28 to Day -2	Day -1	Day 1	Day 2	Day 3	...	
	Visit	Hospitalization					Visit	
Content	Informed Consent, Screening	Admission	Study Drug Administration			Discharge		Follow-up Examination

*: A washout period of at least 6 days will be placed between the study drug administrations in Period 1 and Period 2. The examinations scheduled on the day before the study drug administration (Day -1) in Period 2 can be replaced with the follow-up examinations (Day 6) in Period 1, provided that they are scheduled on the same day. If this is the case, the subject will visit the study site 4 times in this study.

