6.2 Justification for Study Design, Dose, and Endpoints

1. Justification for the Study Design

In accordance with the Guideline for Bioequivalence Studies of Generic Products [9], a 2-period, 2-treatment, cross-over design, which allows bio-equivalence evaluation with minimal effect on inter-subject variation, was selected for this study.

2. Justification for the Study Population

The study population will be healthy adult males in accordance with the Guidance on Clinical Investigation of Medicinal Products in the Pediatric Population [10] and the Guideline for Bioequivalence Studies of Generic Products [9].

3. Justification for Dose

Three formulations of TAK-536 tablets (10 mg, 20 mg, and 40 mg) are marketed for adult patients, and TAK-536 pediatric formulations are being developed for infants and children (from 1 year old to less than 6 years old) who have difficulty swallowing these tablets. Weight-based dosing is planned in this age category. The clinically recommended general dose is considered to be lower than the lowest daily dose of 20 mg for adult patients. Considering the above, 10 mg is selected as the dose of the study drug, since a TAK-536 10 mg tablet with the lowest strength is considered to be the most suitable as a standard among the commercial formulations.

4. Justification for the Washout Period

The elimination half-life of TAK-536 after a single administration of TAK-536 10 mg tablet is 13.1 hours. When TAK-536 10 mg was administered once under fasted conditions in a phase 1, single dose study conducted in Japan, plasma TAK-536 concentration was 9 ng/mL at 72 hours after the administration in the subject with detectable plasma TAK-536 levels for the longest duration. It was assumed in accordance with the Guideline for Bioequivalence Studies of Generic Products [9] that the plasma TAK-536 level would be below the lower limit of quantification

(<1 ng/mL) at 65.5 hours, which is equivalent to 5 times the elimination half-life (13.1 hours), after this time point (72 hours). The duration of washout period in this study will therefore be at least 6 days, in which drug is considered to be eliminated in living body.

5. Justification for the Endpoints

1) Justification for the Pharmacokinetic Endpoints

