13.2 Interim Analysis and Criteria for Early Termination

Interim analysis will be conducted due to judgment of necessity of an add-on subject study for the bioequivalence for TAK-536 commercial formulation and TAK-536 pediatric formulation.

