Appendix A Schedule of Study Procedures (Period 1 and Period 2)

Element	Screening		Treatment (a)				
	Study Day	Day -28 to Day -2 (Screening Visit)	Day -1 (Admission)	Day 1	Day 2	Day 3 (Discharge)	Early Termination
Hospitalization		X		X	X		
Informed consent	X						
Inclusion/exclusion criteria (c)	X			X			
Demographics and medical history	X						
Medication history	X						
Physical examination (d)	X		X	X	X	X	X
Vital signs (e)	X			X	X	X	X
Weight/BMI/height (f)	X			X		X	X
Concomitant medications	X		X	X	X	X	X
Resting 12-lead ECGs (g)	X			X		X	X
Laboratory tests (h)	X			X	X	X	X
Immunology and urine drug tests	X						
Study drug administration				X			
Plasma concentrations(i)				X	X	X	X (j)
AE assessment (k)	X		X	X	X	X	X

AE: Adverse event, ECG: Electrocardiogram

(a) A washout period of at least 6 days will be placed between the study drug administrations in Period 1 and Period 2.

(b) The examinations scheduled on the day before the study drug administration (Day -1) in Period 2 can be replaced with the follow-up examinations (Day 6) in Period 1, provided that they are scheduled on the same day.

(c) Inclusion/exclusion criteria will be confirmed at Screening and before the study drug administration in Period 1, but will not be confirmed on Day 1 in Period 2.

(d) Physical examination will be performed at Screening, Day -1, predose, 4, 24, 48 hours postdose and Day 6.

(e) The sitting blood pressure (resting more than 5 minutes), sitting pulse, and body temperature (axillary) will be measured at Screening, predose, 4, 24 and 48 hours postdose, and Day 6.

(f) The subjects are weighed at Screening, predose, 48 hours postdose, and Day 6. Height is measured only at screening for calculation of BMI.

(g) The resting 12-lead ECG will be measured at Screening, predose, 48 hours postdose and Day 6.

(h) Laboratory tests include hematology, serum chemistry, and urinalysis. Samples will be collected at Screening, predose, 24, 48 hours postdose and Day 6.

(i) Blood samples for PK assessments will be collected at predose (from waking-up to immediately before the study drug administration), 0.5, 1, 1.5, 2, 2.5, 3, 3.5, 4, 5, 6, 8, 12, 16, 24, and 48 hours postdose.

(j) The blood samples for plasma drug concentration measurement should be collected and analyzed only in the case of early termination within 48 hours after the study drug administration.

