(k) Collection of AEs will commence from the time the subject signs the informed consent. Routine collection of AEs will continue until the follow-up examination in Period 2.

Acceptable Time Windows for Study Procedures

Safety Tests/Observations (Period 1 and Period 2)

As per the Protocol		Acceptable Time Window
Tests/Observation Item	Designated Time Window	
Physical examination	Screening	From 28 days to 2 days before the study drug administration
	Day -1	same as on the left
	Before the study drug administration	From waking-up to immediately before the study drug administration
	4 hours postdose	±30 minutes
	24 and 48 hours postdose	±120 minutes
	Follow-up examination (Day 6)	±1 day
Height	Screening	From 28 days to 2 days before the study drug administration
Weight	Screening	From 28 days to 2 days before the study drug administration
	Before the study drug administration	From waking-up to immediately before the study drug administration
	48 hours postdose	±120 minutes
	Follow-up examination (Day 6)	±1 day
Vital sign (sitting blood pressure, sitting pulse, and body temperature)	Screening	From 28 days to 2 days before the study drug administration
	Before the study drug administration	From waking-up to immediately before the study drug administration
	4 hours postdose	±30 minutes
	24 and 48 hours postdose	±120 minutes
	Follow-up examination (Day 6)	±1 day
Resting 12-lead ECGs	Screening	From 28 days to 2 days before the study drug administration
	Before the study drug administration	From waking-up to immediately before the study drug administration
	48 hours postdose	±120 minutes
	Follow-up examination (Day 6)	±1 day
Laboratory tests (Blood)	Screening	From 28 days to 2 days before the study drug administration
	Before the study drug administration	From waking-up to immediately before the study drug administration
	24 and 48 hours postdose	±120 minutes
	Follow-up examination (Day 6)	±1 day
Laboratory tests (Urine)	Screening	From 28 days to 2 days before the study drug administration
	Before the study drug administration	From waking-up to immediately before the study drug administration
	24 and 48 hours postdose	From waking-up to +120 minutes
	Follow-up examination (Day 6)	±1 day

Pharmacokinetics Test/Observations (Period 1 and Period 2)

As per the Protocol		Acceptable Time Window
Tests/Observation Item	Designated Time Window	
Plasma drug concentration	Before the study drug administration	From waking-up to immediately before the study drug administration

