## **7.2 Analysis Sets**

- Pharmacokinetic (PK) Analysis Set: All subjects who received the study drug, completed the minimum protocol-specified procedures without any major protocol deviations, and were evaluable for pharmacokinetics
  - Any subject who meets the following criteria will be excluded from this analysis set:
    - 1) Deviations of protocol entry criteria
      - Deviations of inclusion criteria
        - Inclusion criteria 3, 4, and 5
        - Deviations of exclusion criteria
          - Exclusion criteria 2, 4, 6, 7, 8, 9, 10, 11, and 17

- 2) Deviations related to treatment procedure or dose
  - Deviations related to dose
    - Deviations of dosage

Subjects who received a dose of the study drug other than the doses specified in the protocol
    - Deviations of regimen

Deviations of dosing interval (number of days for washout)  
Subjects who received the study drug in Period 2 without undergoing a washout period of more than 6 days after the study drug administration in Period 1
    - Deviations of dosing conditions

Subjects who did not orally receive a single dose of any study drug under fasted conditions in the morning (fasted for more than 10 hours before the study drug administration)
- 3) Deviations concerning excluded medication or therapy
  - Deviations concerning concomitant medications
    - Administration of excluded medication

Subjects who consumed drugs (prescribed or over-the-counter drugs) described in Table 7. a “Prohibited Medications, Supplements, Dietary Products or Food Products” of the protocol’s section 7.3 within the given time
- 4) Deviations concerning pharmacokinetic measurements
  - Plasma drug concentration
    - No conduct/missing of examinations and assessments concerning pharmacokinetic variables

Subjects whose plasma drug concentration data of TAK-536 was missing or not used at more than 1 visit
- 5) Others
  - Matters of subject management
    - Matters concerning foods and beverages

Subjects who consumed meals other than the provided meals during hospitalization

Subjects who consumed meals within 10 hours before the study drug administration

Subjects who consumed meals within 4 hours after the study drug administration

Subjects who consumed beverages other than water (200 mL) with the study drug from 1 hour before to 4 hours after the study drug administration

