## 7.2 Analysis Sets

- Pharmacokinetic (PK) Analysis Set: All subjects who received the study drug, completed the minimum protocol-specified procedures without any major protocol deviations, and were evaluable for pharmacokinetics
  - Any subject who meets the following criteria will be excluded from this analysis set:
    - 1) Deviations of protocol entry criteria
      - Deviations of inclusion criteria
        - Inclusion criteria 3, 4, and 5
        - Deviations of exclusion criteria
          - Exclusion criteria 2, 4, 6, 7, 8, 9, 10, 11, and 17
      - 2) Deviations related to treatment procedure or dose
        - Deviations related to dose
          - Deviations of dosage
            - Subjects who received a dose of the study drug other than the doses specified in the protocol
          - Deviations of regimen
            - Deviations of dosing interval (number of days for washout)

Subjects who received the study drug in Period 2 without undergoing a washout period of more than 6 days after the study drug administration in Period 1

Deviations of dosing conditions

Subjects who did not orally receive a single dose of any study drug under fasted conditions in the morning (fasted for more than 10 hours before the study drug administration)

3) Deviations concerning excluded medication or therapy

- Deviations concerning concomitant medications

Administration of excluded medication

Subjects who consumed drugs (prescribed or over-the-counter drugs) described in Table 7. a “Prohibited Medications, Supplements, Dietary Products or Food Products” of the protocol’s section 7.3 within the given time

4) Deviations concerning pharmacokinetic measurements

- Plasma drug concentration

No conduct/missing of examinations and assessments concerning pharmacokinetic variables

Subjects whose plasma drug concentration data of TAK-536 was missing or not used at more than 1 visit

5) Others

- Matters of subject management

Matters concerning foods and beverages

Subjects who consumed meals other than the provided meals during hospitalization

Subjects who consumed meals within 10 hours before the study drug administration

Subjects who consumed meals within 4 hours after the study drug administration

Subjects who consumed beverages other than water (200 mL) with the study drug from 1 hour before to 4 hours after the study drug administration

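### SAP 7.2 (final and interim) drops subjects whose washout is exactly 6 days, an interval the protocol permits

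*SAP*

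**What the plan says.** Protocol 6.1 (item 5) states: "A washout period of at least 6 days will be placed between the study drug administrations in Periods 1 and 2". The washout justification in Protocol 6.2 concludes: "The duration of washout period in this study will therefore be at least 6 days". Appendix A, footnote (a), repeats it: "A washout period of at least 6 days will be placed between the study drug administrations in Period 1 and Period 2". The protocol summary has the same minimum, and section 4.4 of both the final and the interim SAP repeats the 6.1 sentence.

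Section 7.2 of both SAPs lists who is removed from the PK analysis set. Under deviations of dosing interval, expressed as a number of days, it names subjects dosed in Period 2 "without undergoing a washout period of more than 6 days after the study drug administration in Period 1".

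Protocol 6.1 also says the Period 2 Day -1 examinations "can be replaced with the follow-up examinations (Day 6) in Period 1, if they are scheduled on the same day". SAP 7.1.3 has a data-handling rule for that case. SAP 7.13 states that the SAP's analysis plan is the same as the protocol's.

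**The concern.** The protocol's limit includes 6 days and the exclusion rule's limit does not. A subject with an interval of exactly 6 days has followed the protocol, yet the SAP classes him as a dosing-interval deviator. This is not a remote case: 6 days is the shortest interval the protocol allows, and the merged visit leads to it.

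The PK set is the only analysis set for the bioequivalence comparison (SAP 7.9.1.4). It is also the set for the interim analysis, whose purpose is given in Protocol 13.2: "Interim analysis will be conducted due to judgment of necessity of an add-on subject study for the bioequivalence". Removing compliant subjects widens the 90% confidence interval in both analyses and makes an add-on study, capped at 120 subjects, more likely. Subjects lost after the Period 1 dose are not replaced (Protocol 7.6), and the 14 planned subjects leave a margin of only two over the 12 used in the power calculation.

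**Working it through.** **1. The plan's own washout figure.** Protocol 6.2 gives a half-life of 13.1 h, a last detectable level of 9 ng/mL at 72 h, and a quantification limit of 1 ng/mL.

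- 5 × 13.1 h = 65.5 h
- 72 h + 65.5 h = 137.5 h, and 137.5/24 = 5.73 days, rounded up to 6 days (144 h)
- Level at 144 h: 9 × 0.5^((144 − 72)/13.1) ≈ 0.2 ng/mL, below 1 ng/mL

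The 6-day minimum reproduces. On the protocol's own reasoning exactly 6 days is long enough, so there is no pharmacokinetic ground for a stricter cut-off.

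**2. Interval under the merged visit.** The Period 1 dose is on Day 1. If the merged visit is on Period 1 day d, the Period 2 dose is on day d + 1 and the interval is (d + 1) − 1 = d days. Appendix A gives the follow-up visit a window of ±1 day.

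| Merged visit on | Interval | Protocol (≥ 6 days) | SAP 7.2 (> 6 days) |
|---|---|---|---|
| Day 5 | 5 days | fails | fails |
| Day 6 (nominal) | 6 days | passes | **fails** |
| Day 7 | 7 days | passes | passes |

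The two rules disagree only at 6 days, which is the nominal case.

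**3. Effect on power.** From Protocol 13.3: true ratio 0.95, limits 0.80 to 1.25, one-sided 5%, two endpoints, variability figures 0.13 (Cmax) and 0.08 (AUC48). The documents call these figures a residual sum of squares, which does not settle how they enter the calculation, so two readings are assumed:

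- (a) within-subject SDs: s = 0.13 and 0.08
- (b) residual sums of squares on 10 df (n = 12): s = √(0.13/10) = 0.114 and √(0.08/10) = 0.0894

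The calculation is exact power of the two one-sided t-tests in a 2×2 crossover, with df = n − 2 and SE = s × √(0.5 × (1/n1 + 1/n2)). Losses are split as evenly as possible between sequences. Joint power is the product of the two endpoint powers, which assumes independence.

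| n (split) | (a) Cmax / AUC48 | (a) joint | (b) Cmax / AUC48 | (b) joint |
|---|---|---|---|---|
| 14 (7+7) | 0.950 / 1.000 | 95.0% | 0.982 / 0.999 | 98.2% |
| 12 (6+6) | 0.913 / 0.999 | 91.2% | 0.963 / 0.997 | 95.9% |
| 11 (6+5) | 0.883 / 0.998 | 88.1% | 0.944 / 0.993 | 93.8% |
| 10 (5+5) | 0.849 / 0.997 | 84.6% | 0.922 / 0.988 | 91.1% |
| 9 (5+4) | – | – | 0.884 / 0.976 | 86.3% |

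At n = 12 both readings agree with the plan's claim of more than 90%. Joint power first falls below 90% at n = 11 under (a), the third exclusion, and at n = 9 under (b), the fifth.

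These crossing points do not depend on independence. Joint power cannot exceed Cmax power alone, which is 88.3% at n = 11 under (a) and 88.4% at n = 9 under (b). It cannot be lower than the sum of the two powers minus 1. One exclusion earlier, that bound is 0.913 + 0.999 − 1 = 91.2% at n = 12 under (a) and 0.922 + 0.988 − 1 = 91.0% at n = 10 under (b).

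**The case against.** The best counter-argument is that this is loose drafting with an obvious intended meaning. The rule sits under a heading for deviations, and exactly 6 days is not one. SAP 4.4 states the inclusive limit and SAP 7.13 declares no departure from the protocol. The documents also mix the two forms elsewhere: fasting is more than 10 hours in Protocol 6.1 but at least 10 hours in Protocol 7.4. This makes an unintended slip the likely explanation. It does not change the exclusion rule as written, and an analyst in an open-label study would have to choose between applying that rule and departing from it.

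A second argument is that nobody may be affected. Merging visits is optional, five visits is the default, no Period 2 dates are given, and intervals of 7 days or more pass both rules. That stands, and it is why the number affected can only be put at 0 to 14. With one site and 14 subjects, scheduling could also make the problem nearly all-or-none, in which case the table's gradual losses are less relevant than the extremes. An almost empty PK set would be noticed, but only after the data exist.

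Third, if the interval were counted in clock time, a subject dosed minutes later in the day in Period 2 would pass. Section 7.2 counts days, however, and a clock-time reading would make inclusion turn on minutes.

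Finally, the 120-subject figure is a feasibility cap, not an expected add-on size. That is correct, and it is used here only as the upper limit.

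**Conclusion.** The concern holds. Section 7.2 of both SAPs sets an exclusion limit that contradicts the protocol and the SAPs' own section 4.4, and the schedule the documents allow can produce exactly the interval in dispute. Applied as written, the rule removes compliant subjects from the only set behind the bioequivalence decision and the interim decision on an add-on study.

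The size depends on how many subjects are dosed exactly 6 days apart, which the documents do not tell us. Up to two exclusions (SD reading) or four (sum-of-squares reading) leave joint power above 90% at a ratio of 0.95; one more takes it below. If all 14 followed the nominal merged schedule, no subject would remain for the primary analysis. These figures rest on the two assumed readings of the variability inputs and on near-even losses between sequences. The cost is precision and possibly an avoidable add-on study.

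**What to change.** In section 7.2, item 2, of both the final and the interim SAP, replace *more than 6 days* with *at least 6 days*, and state that the interval is counted from the Period 1 dosing date to the Period 2 dosing date. Do this before the interim database lock, so that PK-set membership is settled before it can affect either analysis.

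The cost is one line in each SAP. Trial conduct, sample size, significance level and the analysis model do not change.

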7.3 Excluded Medications, Supplements, Dietary Products

Use of the concomitant drugs (prescribed or over-the-counter [OTC] drugs) and consumption of dietary products listed in [Table 7.a](#) is prohibited until the specified period.

Table 7.a Prohibited Medications, Supplements, Dietary Products or Food Products

From 4 weeks (28 days) before the study drug administration in Period 1 to the day of discharge (Day 3) in Period 2	From 72 hours before the study drug administration to the day of discharge (Day 3) in each period
Concomitant Drugs (prescribed or OTC drugs)	Foods and beverages containing grapefruit (juice, pulp), Seville-type (sour) oranges, pineapple (juice, pulp), caffeine or alcohol
Vitamins, Chinese herbal medicines, dietary products containing St. John's wort, Korean ginseng, kava kava, ginkgo, or melatonin	

OTC: over-the-counter

Subjects must be instructed not to take any medications including OTC products, without first consulting with the investigator or sub-investigator. Use of prohibited concomitant drugs will be allowed when the investigator or sub-investigator deem it necessary to use any of the concomitant drugs for reasons including treatment of an AE.

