9.1.10 Pharmacokinetic Sample Collection

9.1.10.1 Collection of Plasma for Pharmacokinetic Sampling

Blood samples (one 3-mL sample per scheduled time) for pharmacokinetic analysis of TAK-536 will be collected into Vacutainers containing ethylenediaminetetraacetic acid dipotassium salt dihydrate (EDTA) according to the schedule in [Appendix A](#). Instructions for sample processing and shipment are provided in a separately defined "Procedure for Handling Samples for Drug Concentration Measurement".

Blood samples for determination of TAK-536 will be collected according to [Table 9.b](#)

Table 9.b Collection of Blood Samples for Pharmacokinetic Analysis

Analyte	Matrix	Dosing Day	Scheduled Time
TAK-536	Plasma	Day 1 of each period	Predose, 0.5, 1, 1.5, 2, 2.5, 3, 3.5, 4, 5, 6, 8, 12, 16, 24, and 48 hours postdose

The actual time of sample collection will be recorded on the source document and eCRF.

If the subject is prematurely terminating from the study within 48 hours after the study drug administration, the blood sample for TAK-536 will be collected at early termination.

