**Table 7.a Visit Window**

Plasma drug concentration

Visit	Scheduled Study Time	Total Study Time in each time interval (hour)
Predose	Study Time (hour): 0	-5.000 - 0.000
0.5 Hour Postdose	Study Time (hour): 0.5	0.417 - 0.583
1 Hour Postdose	Study Time (hour): 1	0.917 - 1.083
1.5 Hours Postdose	Study Time (hour): 1.5	1.417 - 1.583
2 Hours Postdose	Study Time (hour): 2	1.917 - 2.083
2.5 Hours Postdose	Study Time (hour): 2.5	2.417 - 2.583
3 Hours Postdose	Study Time (hour): 3	2.917 - 3.083
3.5 Hours Postdose	Study Time (hour): 3.5	3.417 - 3.583
4 Hours Postdose	Study Time (hour): 4	3.917 - 4.083
5 Hours Postdose	Study Time (hour): 5	4.917 - 5.083
6 Hours Postdose	Study Time (hour): 6	5.917 - 6.083
8 Hours Postdose	Study Time (hour): 8	7.917 - 8.083
12 Hours Postdose	Study Time (hour): 12	11.917 - 12.083
16 Hours Postdose	Study Time (hour): 16	15.750 - 16.250
24 Hours Postdose	Study Time (hour): 24	23.750 - 24.250
48 Hours Postdose	Study Time (hour): 48	47.750 - 48.250

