Subjects who consumed foods described in Table 7. a “Prohibited Medications, Supplements, Dietary Products or Food Products” of the protocol’s section 7.3 within the given time

Matters concerning smoking

Subjects who smoked during hospitalization

Matters concerning body position

Subjects who took a supine position for 4 hours after the study drug administration, unless it was required for examination.

- Safety Analysis Set: All subjects who received the study drug

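### SAP 7.2 ties PK-set exclusion for prohibited foods and drugs to a window ending on Day 3 rather than at the 48-hour sample, so read inclusively it can drop complete, unaffected profiles

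*SAP*

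**What the plan says.** SAP 7.2 lists criteria that lead to mandatory removal from the PK analysis set. Item 3 covers "Subjects who consumed drugs (prescribed or over-the-counter drugs) described in Table 7. a" of the protocol, and item 5 covers "Subjects who consumed foods described in Table 7. a". Both apply when intake fell within the time set by that table. The interim SAP has the same two items. Neither version refers to the last PK sample or allows case-by-case review.

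Protocol 7.3, Table 7.a, sets two windows:

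- Foods and beverages (grapefruit, sour orange, pineapple, caffeine, alcohol): "From 72 hours before the study drug administration to the day of discharge (Day 3) in each period".
- Drugs, vitamins, herbal medicines and certain dietary products: "From 4 weeks (28 days) before the study drug administration in Period 1 to the day of discharge (Day 3) in Period 2". This is one continuous window that includes the washout.

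Protocol 9.1.10.1 schedules PK samples at "Predose, 0.5, 1, 1.5, 2, 2.5, 3, 3.5, 4, 5, 6, 8, 12, 16, 24, and 48 hours postdose". The SAP's visit-window table accepts the last one at "47.750 - 48.250" hours. Under Protocol 6.1 subjects "will be hospitalized under medical supervision for 4 days (until 48 hours after the study drug administration"). On the washout, Protocol 6.2 says: "The duration of washout period in this study will therefore be at least 6 days".

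**The concern.** The food and drug restrictions protect the concentration profile, but the analysis-set rule built on them runs past the end of that profile. After a morning dose, most of Day 3 follows the last sample, and much of it follows discharge. A subject who drinks coffee that afternoon has already given every sample of the period, yet on an inclusive reading of Day 3 he leaves the PK set with both periods.

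The SAP does not treat comparable restrictions this way. Protocol 7.4 forbids smoking for the whole study, while SAP 7.2 excludes only for smoking during hospitalization. Its rule on meals other than those provided is also confined to hospitalization. Foods and drugs alone keep the longer protocol window.

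The stake is the number of subjects in the bioequivalence analysis, which uses only the PK set (SAP 7.9.1.4). Protocol 7.6 does not replace subjects who discontinue after the Period 1 dose. Protocol 13.3 enrols 14 against 12 in the power calculation, a reserve of two. Missing bioequivalence at the interim analysis can lead to an add-on study of up to 120 subjects.

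**Working it through.** **1. Timing.** The documents say only that dosing is in the morning; 08:00 to 10:00 is assumed here.

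- The 48-hour sample then falls at 08:00 to 10:00 on Day 3, leaving 24 − 10 = 14 to 24 − 8 = 16 hours of Day 3 after it. Day 3 ends 48 + 14 = 62 to 48 + 16 = 64 hours after the dose.
- With the minimum washout, the Period 2 dose is 6 × 24 = 144 hours after the Period 1 dose. The Period 2 food window opens 144 − 72 = 72 hours after the Period 1 dose. This is later than the end of Day 3 (62 to 64 hours), and 72 − 48.25 = 23.75 hours after the latest usable 48-hour sample.

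**2. Which cases qualify.**

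| Intake after the 48 h sample on Day 3 | Could it alter a PK sample? |
|---|---|
| Food or drink, Period 1 | Not Period 1, whose sampling is over. For Period 2 it lies outside the protocol's own 72-hour food window. |
| Food or drink, Period 2 | No. All sampling is over. |
| Drug, Period 2 | No. All sampling is over. |
| Drug, Period 1 | Possibly. It precedes the Period 2 dose and lies inside the continuous drug window. |

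The first three rows are needless exclusions. The fourth is not.

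**3. Power by number evaluable.** Inputs from Protocol 13.3: two one-sided tests at 5%, limits 0.80 and 1.25, true ratio 0.95, and variability values of 0.13 (Cmax) and 0.08 (AUC48). For sequence sizes n1 and n2:

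- df = n1 + n2 − 2
- SE = s × √[½(1/n1 + 1/n2)]
- h = t(0.95, df) × estimated SE
- power = P(ln 0.80 + h ≤ estimate ≤ ln 1.25 − h), with estimate ~ N(ln 0.95, SE²), integrated over the chi-square distribution of the residual variance.

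Joint power is taken as the product for the two parameters. For the two readings tabulated below, the lower bound (sum of the two powers minus 1) agrees within 0.1 percentage point.

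The plan's own figure comes first. With 6 + 6 subjects, df = 10 and t = 1.812. Reading the values as residual SDs, SE = 0.13 × √(1/6) = 0.0531 for Cmax and 0.08 × √(1/6) = 0.0327 for AUC48. Power is 91.3% and 99.9%, jointly 91.2%, which reproduces the stated power above 90%. The documents call 0.13 and 0.08 residual sums of squares. Taken literally, and assuming 10 df, the SDs are √(0.13/10) = 0.114 and √(0.08/10) = 0.089, and joint power is 95.9%. Read as variances they give 0.8%, which is incompatible with the plan.

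| Evaluable (split) | Joint power, SD reading | Joint power, literal sum-of-squares reading |
|---|---|---|
| 14 (7+7) | 95.0% | 98.1% |
| 13 (7+6) | 93.2% | 97.2% |
| 12 (6+6) | 91.2% | 95.9% |
| 12 (7+5) | 90.5% | 95.5% |
| 11 (6+5) | 88.1% | 93.8% |
| 10 (5+5) | 84.6% | 91.1% |

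**4. How likely are three exclusions?** The documents give no rate. For an assumed probability p per subject, P(at least 3 of 14) = 1 − Σ(k = 0 to 2) C(14,k) p^k (1 − p)^(14−k). This is 0.2% at p = 2%, 3.0% at 5% and 15.8% at 10%.

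**The case against.** The strongest reply is that Table 7.a gives no clock time. Hospitalization ends at 48 hours, so the window could be meant to close at discharge, leaving little or nothing after the last sample. That reading is possible. The inclusive reading is the more natural one for a window that ends on a named day, but the text does not settle it, and removal from the primary analysis should not depend on which reading is chosen.

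A second reply is that a fixed rule matching the protocol's prohibition is simple and prespecified, and avoids case-by-case judgement in an open-label study. That has merit, but a cut-off at the last sample is equally fixed and can be prespecified too.

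Third, Protocol 7.5 lists the same intake as a reason for discontinuation. A subject withdrawn in Period 1 never yields a second profile, so SAP 7.2 would then delete no pair. This narrows the Period 1 food case without removing it: Protocol 7.6 says the investigator may discontinue such a subject, whereas the SAP exclusion is mandatory.

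A reader might infer three stronger points, none of which the documents support:

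- That drug use after the 48-hour sample is harmless in Period 1 as well. It is not clearly so, because the drug prohibition runs through the washout up to and past the Period 2 dose.
- That the rule biases the comparison, because Protocol 7.3 permits drugs needed to treat an adverse event and item 3 makes no exception for them. PK-set membership can then depend on a post-dose event, but no link between such exclusions and the formulation ratio is shown.
- That the trial would fall below its stated power. That takes three losses and the SD reading, and the plan already provides an add-on study.

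**Conclusion.** The point holds as a narrow gap in the definition of the PK set. If Day 3 counts in full, SAP 7.2 removes subjects for intake that cannot have affected the relevant profiles: foods or beverages after the 48-hour sample in either period, and drugs after the 48-hour sample in Period 2.

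The cost is conditional on such intake occurring. Under the SD reading, one exclusion costs just under 2 percentage points of joint power, two keep it above 90%, and a third brings it to 88.1%. Under the literal sum-of-squares reading, 11 subjects still give 93.8%. No figure in the plan is wrong. This is a low-priority improvement, worth making because it costs almost nothing and keeps valid primary data.

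**What to change.** Before the interim database lock, amend SAP 7.2 in both the final and the interim SAP:

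- **Item 5, foods and beverages:** intake triggers PK exclusion from the start of the Table 7.a window to the 48-hour PK sample of that period.
- **Item 3, drugs:** intake triggers PK exclusion from the start of the Table 7.a window, through the washout, to the 48-hour PK sample of Period 2. Vitamins, herbal medicines and dietary products that share the drugs' column should follow this same window.
- Later intake that still falls within Table 7.a remains listed as a protocol deviation.

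The protocol's restrictions on subjects do not change. The cost is a short text edit, a slightly less simple rule, and the need for intake times on Day 3. For drugs, Protocol 9.1.6 lists only start and end dates, so a time would have to be asked for when intake falls on that day.
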